### **Capecitabine**

In the event of haematological toxicity or other adverse events capecitabine dose may be modified as per standard of care (treatment interruption or dose reduction). Dose adjustments are to be made according to the greatest degree of toxicity and in accordance with the local hospital protocol. Once the dose has been reduced, it should not be increased at a later time.

## **8.6 Compliance**

### **Enadenotucirev**

All doses of enadenotucirev will be delivered intravenously at a research site. Site staff will maintain records of enadenotucirev administration.

### **Capecitabine**

Patients will be instructed to keep a record of compliance with capecitabine treatment, by means of using a patient diary card provided to the patient by the site. Patients should be asked to bring completed diary cards or other records and all their unused / remaining capecitabine tablets (empty, open or unopened) with them to each clinic visit. The patient diary cards should not be sent to the Trial Office but kept by the centre to monitor patient drug compliance.

Accountability logs are required for capecitabine to determine that patients have received at least 80% of the prescribed treatment dose. Returns should be reconciled against the patient diary and the reason for any discrepancy documented. Site staff will collect and count patient returns which must be recorded on the drug accountability log.

## **8.7 Management of overdose**

In the case of enadenotucirev overdose the patient should be monitored for evidence of toxicity and standard supportive treatment provided based on any signs or symptoms experienced.

In the case of capecitabine overdose refer to guidance provided in the SPC.

Administration of a dose of trial drug exceeding that permitted by the trial protocol should be notified to the trial office. Any toxicity resulting from administration of an overdose of trial drug should also be reported as an adverse event/ serious adverse event (as appropriate) as per reporting processes detailed in section 14.

## **9 DOSE LIMITING TOXICITY**

### **9.1 Definition of a dose limiting toxicity (DLT)**

All patients who have received at least one dose of enadenotucirev will be evaluable for DLTs. DLTs are defined as any of the following occurring between the start of trial treatment until the Week 13 visit and by the principal investigator (PI) or agreed designee assessed as possibly, probably or definitely related to enadenotucirev or the interaction between enadenotucirev and radiotherapy and/or capecitabine. Patients who experience a DLT will receive no further trial treatment.

Dose limiting toxicities must be reported within 24 hours of the site becoming aware using the SAE form and scan and email as a PDF attachment to [[contact]](mailto:[contact]) and send an email notification to [[contact]](mailto:[contact]).

DLTs will be defined as per NCI CTCAE v4.03, except for proteinuria, and include:

#### **Renal:**

- Development of proteinuria, 2+ as measured by urinalysis and confirmed with an albumin/creatinine ratio of  $>3\text{g}/\text{mmol}$  with a 24-hour urinary protein  $\geq 1\text{g}/24\text{h}$  or if there is a decline in eGFR (where a decline in eGFR is defined as eGFR  $<60\text{ml}/\text{min}/1.73\text{m}^2$  or a drop in eGFR by 20% from screening, baseline or previous visit), following administration of enadenotucirev, shall be classified as a DLT. No further doses of enadenotucirev will be administered to that patient.

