**and**
  - Urine dipstick for proteinuria at screening and baseline negative or trace. Patients may be included with results of 1+ if they have a spot urinary albumin creatinine ratio (ACR) of either:
    - (i)  $\leq 3$  mg/mmol **or**
    - (ii)  $>3$  mg/mmol with a 24 hour urinary protein  $<1.0$  g/24hours  

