#### 5.3.1 Evaluation schedule A

**Pre- Dose – the following assessments can be completed within 72 hours prior to the dose. Vital signs to be completed on day of dosing**

- Adverse events and DLTs since the previous assessment
- New or changes to existing medications
- Physical examination of major body systems
- Weight
- ECOG performance status
- Local laboratory assessments:
  - Urine dipstick – if 2+ or greater proteinuria enadenotucirev dosing should be interrupted pending completion of 24 hour urine collection to exclude significant proteinuria, see further guidance in section 9.3.

- Routine blood samples
  - Haematology – Hb, white blood cells (WBC) with differential count (neutrophils and lymphocytes) and platelets
  - Biochemistry – sodium, potassium, calcium, phosphate, urea, creatinine, total protein, albumin, bilirubin, alkaline phosphatase (alk phos), AST and/or ALT and LDH
  - Coagulation screen (aPTT and INR)

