**General:**

- Discontinuation of the active treatment due to toxicity definitely attributable to enadenotucirev, irrespective of the grade of toxicity
- Missing 3 consecutive fractions of radiotherapy, related to enadenotucirev, as judged by the PI or designee
- Any toxicity causing a delay of radiotherapy completion by greater than one week

This is not an exhaustive list. All suspected DLTs should be discussed with the Chief Investigator and the Trial Management Group.

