**Renal injury:** Three patients out of 123 patients (2.4%) have developed significant renal impairment while receiving enadenotucirev. Whilst no confirmed pathophysiology has been identified it is felt to be due to vascular leakage due to cytokine release. Proteinuria of 2+ on a urine dipstick should therefore be further investigated, due to the potential risk of serious renal injury, with 24 hour urine collection for protein/creatinine ratio. If preferable locally, a urine protein- to-creatinine ratio or urine albumin – to – creatinine ratio are also acceptable in lieu of a 24 hour collection test. Additional blood tests should also be up to date including a serum albumin and serum creatinine. A consultation with nephrology is advised for specialist input. Specifically, early specialist intervention for investigation and treatment if decline in renal function is detected will include:

1. Full renal work-up, including examination of urine sediment, discussion with renal team and then commence high dose corticosteroids and then, if further decline in renal function;
2. Renal biopsy, followed by plasmapheresis should be considered with close involvement of the renal team.

No enadenotucirev is to be administered after the development of proteinuria as this constitutes a DLT.

Refer to section 8.5 for guidance on dose modification/ interruption due to toxicity.

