Medically important events in the context of this trial (considered dose limiting and possibly, probably or definitely related to enadenotucirev combined with Radiotherapy +/- chemotherapy)		Email reporting form within 24 hours	Report in AE CRF	Non reportable
Any AE not listed above that is grade $\geq 3$	X	X	X	
AE considered more severe than expected	X	X	X	

AE Grade <3 that is unexpected and thought to be directly treatment related to the combination of enadenotucirev with radiotherapy +/- chemotherapy	X	X	X	
AE resulting in withdrawal	X	X	X	
Any late grade $\geq 3$ toxicities – onset 12 weeks after completion of radiotherapy	X	X	X	
Any late grade 2 toxicities – onset 12 weeks after completion of radiotherapy			X	
Acute Hypersensitivity reaction to enadenotucirev	X	X	X	
Expected non-dose limiting toxicities	Email reporting form within 24 hours		Report in AE CRF	Non reportable
See section 9.2		If grade $\geq 4$	X	
All other AEs, abnormal assessments or laboratory results	Email reporting form within 24 hours		Report in AE CRF	Non reportable
All other AEs, assessments, abnormal laboratory results, if clinically significant		If grade $\geq 3$	X	
AE is life-threatening		X	X	
AE requires in-patient hospitalisation or prolongs existing inpatient hospitalisation		X	X	
AE results in persistent or significant incapacity or disability		X	X	
AE is a congenital anomaly or birth defect		X	X	
AE is any other medically important event		X	X	
AE related to surgery (wound dehiscence, life threatening complication requiring ICU management, single organ dysfunction including dialysis)		X	X	
Disease progression and resultant death	Email reporting form within 24 hours		Report in AE CRF	Non reportable
Hospitalisation (for progression or procedures planned prior to informed consent )				X
Clinical symptoms of progression				X
Death		Possibly related directly to enadenotucirev or the combination of enadenotucirev + radiotherapy +/- chemotherapy	Report death and reason on death notification CRF	

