# 6. ANALYSIS

## 6.1 Outcome Definitions

Primary outcome:

- *Safety*: Binary toxicity measure defined by the occurrence of a DLT or not. This is recorded during the 13 weeks of follow-up after starting treatment. The definition of a DLT is given Appendix 4.
- *Efficacy*: MRI tumour regression grade. This is a 5 point scale that is coded as a binary variable, with scores of 1 or 2 defining a responder and scores of 3, 4 or 5 a non-responder. It is measured at 13 weeks. Patients who did not have the evaluation, or who withdrew or died prior to evaluation will be treated as non-responders. During the trial, for dose-escalation decisions a patient who has not yet reached this time point will not be included in analysis at this decision point. See Appendix 5 for the definition of MRI tumour regression grade

See Section 6.2.1 Primary analysis for definition of the optimal dose.

For dose-escalation interim analyses the safety and efficacy data is taken from the patient status update CRF. For the final determination of the MTD at the end of the trial, the safety outcome will be taken from the *BW135\_DLT\_Assessment* and *BW166\_Adverse\_Events* CRFs and the efficacy outcome taken from the *BW156\_Week13\_Pelvic\_MRI* CRF.

Secondary outcomes:

- Treatment tolerance. This is the amount of capecitabine and radiotherapy received, coded as completing at least 80% of the intended capecitabine dose and at least 20 fractions of radiotherapy. Measured at week 9. Compliance is taken from the *BW150\_Capecitabine* and *BW145\_Radiotherapy* CRF.
- MRI tumour regression grade. See definition for primary outcome, but here it will not be dichotomised. MRI tumour regression grade is taken from the *BW156\_Week13\_Pelvic\_MRI* CRF.
- Pathological complete response. This variable relates to the resected tumour so will only be observed for patients undergoing surgery. It is measured on a 4 point scale, with a score of 1 denoting pathological complete response, and scores 2:4 denoting no pathological complete response. Pathological complete response is taken from the *BW156\_Week13\_Pelvic\_MRI* CRF.
- Neoadjuvant Rectal (NAR) score. This score ranges from 0-100 with a higher score equating to a worse prognosis. It is a derived outcome which components measured on the resected tumour and at initial tumour staging. Therefore, this will only be observed for patients undergoing surgery. It is defined as

- $NAR = \frac{[5pN - 3(cT - pT) + 12]^2}{9.61}$ , where

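### The renal DLT ratio is printed as >3 g/mmol in Protocol 9.1 and SAP Appendix 4, 1000 times the 3 mg/mmol of inclusion criterion 8, and 9.3 admits a ratio test with no cut-off

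*Protocol*

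**What the plan says.** - **Protocol 9.1, Renal.** The DLT is "Development of proteinuria, 2+ as measured by urinalysis and confirmed with an albumin/creatinine ratio of" >3 g/mmol with 24-hour urinary protein of at least 1 g, or a decline in eGFR (below 60 ml/min/1.73m², or a 20% drop).
- **SAP 6.1 and Appendix 4.** SAP 6.1 states: "The definition of a DLT is given Appendix 4". The renal item in Appendix 4 has the same >3 g/mmol and no 24-hour or eGFR element. The appendix says that it reproduces protocol V3.0.
- **Protocol 4.1, inclusion criterion 8.** A 1+ patient may enter with an albumin/creatinine ratio (ACR) of at most 3 mg/mmol, or above 3 "mg/mmol with a 24 hour urinary protein" below 1.0 g.
- **Protocol 9.3, renal injury.** A 2+ dipstick leads to a 24-hour collection. Protein/creatinine or albumin/creatinine ratios "are also acceptable in lieu of a 24 hour collection test". No cut-off is given for any of these tests. The paragraph ends: "No enadenotucirev is to be administered after the development of proteinuria as this constitutes a DLT".
- **Protocol 5.3.1.** Dosing is interrupted at 2+ pending "24 hour urine collection to exclude significant proteinuria, see further guidance in section 9.3". This is a dosing hold, not another DLT definition.

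**The concern.** DLT status is a primary endpoint and the outcome variable of the toxicity model. Protocol 9.1 grades DLTs by CTCAE except for proteinuria, so the renal item is the intended proteinuria criterion, and its threshold has the wrong unit in both governing documents.

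Protocol 9.3 does not repair this. It admits a different test, supplies no number for it, and does not refer back to 9.1. Two sites following the protocol could record the same patient differently.

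The table in 9.2 lists treatment-related proteinuria in 0% of patients at 1x10^12 vp and 20% at 3x10^12 vp. That suggests such cases would arise more on schedules 3 and 4, which use the higher dose. It is only an indication: the table shows no grades or denominators and does not describe patients on chemoradiotherapy.

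**Working it through.** **1. Unit.** 3 g/mmol x 1000 mg/g = 3000 mg/mmol. Against criterion 8: 3000 / 3 = 1000.

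**2. Plausibility.** Daily creatinine excretion is not in the documents. Assume 8 to 15 mmol/day.

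| Threshold | Formula | Result |
|---|---|---|
| 3 g/mmol as printed | 3 x 8 to 3 x 15 | 24 to 45 g albumin/day |
| 3 mg/mmol | 3 x 8 to 3 x 15 | 24 to 45 mg albumin/day |
| 1 g protein/24 h as a ratio | 1000/15 to 1000/8 | 67 to 125 mg/mmol |

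The printed ratio needs 24 to 45 times the 1 g/24 h required in the same sentence. With the unit corrected, the ratio is the mild condition and the 24-hour protein decides. This matches criterion 8, where ACR above 3 mg/mmol is tolerated as long as 24-hour protein stays below 1.0 g.

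**3. Why the unit alone is not enough.** If a ratio replaces the 24-hour collection and only ACR >3 mg/mmol remains, the test is looser than 1 g/24 h by about 67/3 = 22 to 125/3 = 42 times. This is approximate, because it compares albumin with total protein.

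**4. The definitions side by side**, for a patient with 2+ proteinuria attributed to enadenotucirev:

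| Work-up | 9.1 as printed | 9.1 in mg/mmol | SAP Appendix 4 as printed | Plain words of 9.3 |
|---|---|---|---|---|
| ACR >3 mg/mmol, 24-hour protein at least 1 g, eGFR stable | not met | DLT | not met | DLT |
| Ratio only, eGFR stable | not met | undecided: 24-hour value missing | not met | DLT |
| eGFR decline | DLT if the eGFR clause stands apart from the ratio | same | no eGFR element | DLT |

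The grammar of 9.1 leaves open whether an eGFR decline replaces only the 24-hour value, replaces the whole confirmation, or counts without 2+.

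**5. Who is left after the missed-dose route.** Under 8.5 and 9.1, missing two consecutive doses through enadenotucirev toxicity is a DLT. Planned doses (8.2) are 3 on schedule 1, 3 + 3 = 6 on schedules 2 and 3, and 3 + 2 + 3 = 8 on schedule 4. The dipstick belongs to evaluation A, not B, so in each block of three it precedes doses 1 and 3.

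- Schedule 1: the first dipstick after a dose comes before dose 3, with 3 - 2 = 1 dose left. Two cannot be missed.
- Schedules 2 and 3: 2+ before loading dose 3 leaves 6 - 2 = 4 doses, so stopping leads to a DLT. 2+ before the last maintenance dose leaves 1.
- Schedule 4: 2+ before the last maintenance dose leaves 8 - 7 = 1.
- Week 13 visit (5.9), all schedules: a dipstick is taken and no doses remain.

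The exposed group is therefore mainly eGFR-stable proteinuria found with at most one dose left, or cleared for re-dosing after work-up.

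**The case against.** The strongest reply is that the slip is obvious and self-correcting. Criterion 8 shows the intended unit beside the same 1 g limit, nobody would apply 24 to 45 g of albumin a day, and 9.1 says "All suspected DLTs should be discussed with the Chief Investigator and the Trial Management Group". Much of this stands. The eGFR and missed-dose routes remain. Table 14.4 adds AEs leading to withdrawal and "Any AE not listed above that is grade" 3 or higher as DLT rows. The withdrawal row may catch some patients whom the missed-dose route cannot. But 14.4 has no proteinuria row, grade-based rows fit poorly with a criterion exempted from CTCAE, and any discussion starts from a wrong written number.

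It is also fair that 9.3 is a management section and can be read as meaning proteinuria confirmed by the work-up it has just described. It does not say so, and under that reading the ratio still has no cut-off.

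Three stronger inferences are tempting and not supported:

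- **That no proteinuria DLT would reach the model, because Appendix 4 is out of reach.** SAP 6.1 takes DLTs from the patient status update CRF during the trial and from the DLT and adverse event CRFs at the end. These are site assessments, not derivations from the appendix text. The missing 24-hour and eGFR elements there may be version lag.
- **That patients would be re-dosed unsafely.** Sections 5.3.1, 8.5 and 9.3 hold or stop dosing at 2+.
- **That the selected dose would be wrong.** One reclassified patient can move the SAP toxicity model. With 2, 2, 6 and 0 patients on schedules 1 to 4, full weights, and no DLTs below schedule 3, going from 1 to 2 DLTs on schedule 3 raises the posterior probability of a DLT rate above 0.35 on schedule 4 from 0.193 to 0.425. That crosses the 0.35 limit, and the toxicity recommendation drops from 4 to 3. Going from 0 to 1 leaves it at 4. Any DLT item would do the same, and nothing in the documents says how often this one would misclassify a patient.

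**Conclusion.** The point holds as a should-fix correction to a primary-endpoint threshold. The factor of 1000 is exact and needs no assumption. That the printed ratio is unreachable, and the 67 to 125 mg/mmol equivalent of 1 g/24 h, both rest on the assumed 8 to 15 mmol creatinine/day.

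The mismatch between 9.1 and 9.3 is real for eGFR-stable 2+ patients tested only by ratio, although 9.3 admits a reading that softens it. Other written routes shrink the affected group. Its remaining size is not in the documents, and no shift in the DLT rate or in dose selection is quantified.

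**What to change.** 1. Change g/mmol to mg/mmol in Protocol 9.1 and SAP Appendix 4.
2. Reword the last sentence of the renal injury paragraph in 9.3 so that it refers to proteinuria meeting the definition in 9.1.
3. Where a ratio replaces the 24-hour collection, have the sponsor set one protein/creatinine cut-off equivalent to 1 g/24 h. The range above is a starting point; the value is a clinical choice. ACR >3 mg/mmol alone should not serve.
4. State whether the eGFR branch in 9.1 needs 2+ or the ratio, or counts alone. Bring Appendix 4 into line with the current 9.1.
5. Recheck recorded 2+ results against the corrected definition before the next model fit.

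The cost is a wording amendment to two protocol sections and one SAP appendix, two sponsor decisions, and a short data check. No patient procedure is added, because 9.3 already allows the ratio.

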#### **Acute hematologic toxicity:**

- Infection (documented clinically or microbiologically) with grade 3 or 4 neutropenia (absolute neutrophil count (ANC)  $<1.0 \times 10^9/\text{L}$ )
- Neutropenia grade 4 (ANC  $< 0.5 \times 10^9/\text{L}$ ) lasting for  $\geq 7$  days

- Febrile neutropenia grade 4 (fever of unknown origin without clinically or microbiologically documented infection) (ANC <1000/mm^3 with a single temperature of >38.3 degrees C or a sustained temperature of >=38 degrees C for more than one hour)
- Thrombocytopenia grade 3 (Platelet count < 50 x 10^9/L) in the presence of bleeding or requiring platelet transfusion
- Thrombocytopenia grade ≥ 4 (Platelet count < 25 x 10^9/L)
- Anemia grade 3 in the presence of blood transfusion dependency as judged by the PI
- Anemia grade ≥ 4
- Clinically significant bleeding attributed to grade 3 thrombocytopenia or requiring platelet transfusion or other grade ≥3 clotting disorder or occurring concurrently with Grade 2 or 3 aPTT prolongation, unless there is a clear explanation for the event, such as tumour-related bleeding in the presence of Lupus Anticoagulant.
- Any other grade ≥3 non-hematological toxicity with the exception of: activated partial thromboplastin time (aPTT) prolongation
- Clotting event (i.e. deep vein thrombosis [DVT], pulmonary embolism [PE]) occurring concurrently with Grade 2 or 3 aPTT prolongation

**Acute non-hematologic toxicity:**

- Any documented ≥ grade 4 non-hematologic toxicity in the presence of maximal support/active management
- Grade ≥3 cystitis or radiation dermatitis onset within 2 weeks of starting radiotherapy or lasting more than 2 weeks after the end of radiotherapy.
- Grade ≥3 proctitis or diarrhea onset within 2 weeks of starting radiotherapy
- Grade ≥3 nausea or vomiting not controlled by optimal outpatient anti-emetic treatment
- Grade ≥3 diarrhea despite optimal outpatient anti-diarrheal medication use
- Grade ≥3 hematuria or neuropathic pain
- Other grade 3 ≥ effects thought to be due to the combination of enadenotucirev with radiotherapy
- Missing 2 consecutive doses of enadenotucirev due to enad toxicity
- An elevation of ALT or AST >5 x ULN lasting 8 days or more
- A concurrent elevation of ALT or AST >3 x ULN and total bilirubin >2 x ULN in whom there is no evidence of biliary obstruction or other causes that can reasonably explain the concurrent elevation
- Death due to drug related complications
- Grade ≥3 cytokine release syndrome

**General:**

- Discontinuation of the active treatment due to toxicity definitely attributable to enadenotucirev, irrespective of the grade of toxicity
- Missing 3 consecutive fractions of radiotherapy, related to enadenotucirev, as judged by the PI or designee
- Any toxicity causing a delay of radiotherapy completion by greater than one week

This is not an exhaustive list. All suspected DLTs should be discussed with the Chief Investigator and the Trial Management Group.

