#### **8.5 Dose modification**

##### **Enadenotucirev**

No dose modifications may be made. **With the exception of renal injury, specifically proteinuria of 2+ where enadenotucirev must be delayed and or discontinued (see section 9.3),** treatment may be interrupted because of a non-DLT of Grade 3 or higher, at the discretion of the Investigator. Treatment may be resumed when all toxicities have returned to grade 2 or less, at the discretion of the Investigator. If two consecutive doses of enadenotucirev are missed due to enadenotucirev related toxicity, this constitutes a DLT, and no further enadenotucirev will be administered. If the subject misses a dose of enadenotucirev for any reason other than toxicity the dose should not be made up. The scheduling should continue as normal, from the next planned dose of enadenotucirev. If radiotherapy is

withheld for toxicity or other reasons, enadenotucirev should also be withheld and the dosing schedule should continue from the next planned dose once radiotherapy has resumed.

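### The documents conflict on whether stopping enadenotucirev for a lower-grade, possibly or probably related toxicity is a DLT, and under the 9.1 list a stop after loading dose 2 is coded differently on schedule 1 than on schedules 2-4

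*Protocol*

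**What the plan says.** Four places in the protocol bear on whether stopping enadenotucirev for toxicity is a DLT.

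- **Opening of 9.1.** An event on the list counts if it is "assessed as possibly, probably or definitely related to enadenotucirev or the interaction between enadenotucirev and radiotherapy and/or capecitabine". The same paragraph says that a patient with a DLT receives no further trial treatment.
- **9.1, General.** The discontinuation line applies at any grade but sets a higher attribution level: "Discontinuation of the active treatment due to toxicity definitely attributable to enadenotucirev, irrespective of the grade of toxicity".
- **9.1, Acute non-hematologic toxicity, and 8.5.** The list includes "Missing 2 consecutive doses of enadenotucirev due to enad toxicity". Section 8.5 agrees: "If two consecutive doses of enadenotucirev are missed due to enadenotucirev related toxicity, this constitutes a DLT, and no further enadenotucirev will be administered". Neither asks for definite attribution.
- **14.4 reporting table.** The row "AE resulting in withdrawal" is marked as a DLT. Its block heading describes the events as "considered dose limiting and possibly, probably or definitely related to enadenotucirev combined with Radiotherapy +/- chemotherapy", with no condition on missed doses.

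SAP 6.1 takes the primary safety outcome from SAP Appendix 4. That appendix repeats the General line with its definite-attribution wording, has the two-missed-doses line (for toxicity, without naming enadenotucirev), and carries over nothing from the 14.4 table.

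**The concern.** Consider a patient who stops enadenotucirev for good because of a grade 1 or 2 toxicity judged possibly or probably related. The opening of 9.1 and the 14.4 row point to a DLT. The General line does not, because attribution falls short of definite. If no other criterion is met, what remains in the 9.1 list and Appendix 4 is the missed-doses line, and whether two doses are left to miss is fixed by the assigned schedule rather than by the patient's tolerance.

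Schedules 1 and 2 both load with three doses of 1 x 10^12 vp. Two patients with the same exposure, the same toxicity and the same decision to stop can therefore receive different values of the primary endpoint. Where they differ, it is schedule 1 that is coded DLT-free. The first escalation decision rests on two patients treated there, so one recoded patient can matter.

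**Working it through.** The documents give no figure for this point that could be reproduced. The simulation results are in SAP Appendix 1, a separate document.

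**1. Doses missed after a permanent stop.** Protocol 8.2 plans 3 doses on schedule 1, 3 + 3 = 6 on schedules 2 and 3, and 3 + 2 + 3 = 8 on schedule 4. Doses missed = planned minus received.

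| Stop after loading dose | Sched. 1 | Sched. 2 | Sched. 3 | Sched. 4 | Two-missed-doses line |
|---|---|---|---|---|---|
| 1 | 2 | 5 | 5 | 7 | met on all |
| 2 | 1 | 4 | 4 | 6 | not met on schedule 1; met on 2-4 |
| 3 | 0 | 3 | 3 | 5 | schedule 1 already complete; met on 2-4 |

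Reading consecutive as within one course changes nothing for schedules 2-4, because their later doses alone include two consecutive misses. So only a stop after dose 2 leaves a schedule 1 patient with treatment cut short and the line not met.

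**2. Grade limit.** The list also contains "Any other grade ≥3 non-hematological toxicity with the exception of: activated partial thromboplastin time (aPTT) prolongation". The gap is therefore mainly grade 1-2 events and haematological events below their own thresholds.

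**3. Weight of the DLT-free coding.** SAP 6.2.1 gives w = ½(u/T + v/D). At week 13, with two of three equal doses received, w = ½(13/13 + 2/3) = 0.833.

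**4. Illustration with the toxicity model.** Inputs from SAP 6.2.1:

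- schedule codes x = 1, 2, 4, 6, with reference 6
- logit(p) = log α + β log(x/6)
- log α ~ N(log(0.3/0.7), variance 1.44) and log β ~ N(-0.1, variance 0.25), uncorrelated

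I used the standard TITE likelihood: w·p for a DLT (w = 1) and 1 - w·p otherwise. This is an assumption, because the SAP formula labels g as the logit. The posterior was computed on a numerical grid.

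Two schedule 1 patients are followed to week 13. One is DLT-free at full weight and the other stops after dose 2. Posterior P(DLT rate > 0.35):

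| Stop coded as | Sched. 1 | Sched. 2 | Sched. 3 | Sched. 4 |
|---|---|---|---|---|
| DLT-free, w = 0.833 | 0.030 | 0.082 | 0.215 | 0.348 |
| DLT | 0.214 | 0.385 | 0.598 | 0.711 |

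The safety criterion requires less than 0.35.

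- **DLT-free:** all four schedules pass. The toxicity model favours schedule 4 (probability 0.266 in the target interval, the highest), and the no-skipping rule holds it to schedule 2.
- **DLT:** only schedule 1 passes, and the model recommends schedule 1.

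**5. Three schedule 1 patients.**

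- **One such stop:** P on schedule 2 is 0.059 (DLT-free) or 0.301 (DLT). Both pass, and the toxicity model leads to schedule 2 either way.
- **Two such stops:** P on schedule 1 is 0.020 or 0.456. Under the DLT coding no schedule meets the safety criterion.

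**The case against.** The strongest reply is that 14.4 already makes the schedule 1 patient a DLT: it has a row for adverse events leading to withdrawal, accepts possible and probable relation, and sets no missed-dose condition. Protocol section 6 lists adverse events requiring discontinuation under treatment withdrawal. This stands, and it rules out a reading that someone working from 9.1 alone might reach: that across the whole protocol such a stop is a DLT only if two doses remain. It does not settle the matter, because SAP Appendix 4 follows the narrower 9.1 list.

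Other replies:

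- **Judgement.** Section 9.1 says that its list is not exhaustive and sends suspected DLTs to the Chief Investigator and the TMG. That allows a correction case by case. It does not make the coding uniform, and an explicit requirement for definite attribution points the discussion away from a DLT.
- **Frequency.** The documents give no rate for such stops. Sections 1.2 and 9.3 say that inflammatory events are less frequent after later doses and that infusion reactions are more common with the first infusion. That suggests stops after dose 1, where the schedules agree. Section 8.5 provides for discretionary interruption at grade 3 or higher, so a permanent stop at grade 2 would come by another route, such as the clinical or patient decision allowed in section 6. These points stand and limit the size.
- **Other brakes on escalation.** Allocation is the minimum of the toxicity and efficacy recommendations, and the TMG may go lower. The sensitivity population excludes a patient who missed a dose without a DLT, so the TMG would see the case. All this stands, although excluding the patient leaves that analysis without the intolerance too.

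**Conclusion.** The conflict is real but narrow. Under the 9.1 list and Appendix 4, one kind of event is coded by schedule: a permanent stop after loading dose 2, for a possibly or probably related toxicity that meets no other criterion. It is DLT-free on schedule 1 and a DLT on schedules 2-4. Under 14.4 it is a DLT on all four. The same patient can thus have two endpoint values under one protocol.

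In a two-patient first cohort, the coding moves P(DLT rate > 0.35) on schedule 2 from 0.08 to 0.39 and reverses the toxicity model's recommendation. This rests on the standard TITE likelihood, on the toxicity model alone and on one hypothetical patient. One more DLT-free patient on schedule 1 brings the higher figure down to 0.30.

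A reader might infer more than the documents support:

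- **That every stop during loading is affected.** A stop after dose 1 is a DLT on every schedule.
- **That the early stopping rule is easily disabled.** It needs P > 0.65 on schedule 1 and at least three patients with complete data. Coding two such stops in three patients as DLTs gives only 0.456. It would take three of three (0.788) or three of four (0.670).
- **That the dose-toxicity curve is distorted by a known amount.** Counting possible stop points does not give a rate, and no rate is stated.
- **That schedule 2 would necessarily open.** The efficacy model or the TMG could still hold the dose down.

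**What to change.** Reconcile the opening of 9.1, the missed-doses line in 9.1 and 8.5, the General discontinuation line and the 14.4 withdrawal row to a single attribution standard. Word it so that the same discontinuation is coded the same way however many doses remain on the schedule. Carry identical wording into SAP Appendix 4, including its missed-doses line.

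The sponsor should decide which standard applies. The choice is more than a coding matter, because under 9.1 a DLT also ends trial treatment. It would help to state how such a DLT is dated: after a stop at loading dose 2 on schedules 2 and 3, the second miss falls only in weeks 8-9, and the documents give no date rule.

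The cost is a few words in each document, plus the amendment procedure that a change to a treatment-stopping definition may require. A few stops may be recoded.
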